5.0 STUDY COHORT

1. Population

Recruitment of 450 WLWH aged 18-45 years is being performed by research staff at 10 sites across Canada. The 450 WLWH will be randomized 1:1 to two groups:

- 1) Three doses of 9vHPV vaccine at the routine dosing schedule of 0/2/6 months.
- 2) Three doses of 9vHPV vaccine at an extended dosing schedule of 0/6/12 months.

Inclusion Criteria

- Has a confirmed diagnosis of HIV infection
- Has a cervix (not have had their uterus removed)
- Age 18-45 years
- Not pregnant, and not trying to become pregnant
- Able to communicate in English if adequate translation is not available

Exclusion Criteria

- Unable to give fully informed consent
- Allergy to the vaccine or its components
- Prior receipt of any HPV vaccine.

Females aged <18 are excluded because all children, including those with HIV, are vaccinated in adolescent programs in Canada leaving very few eligible under that age. Further, we seek to inform the use of 9vHPV vaccine beyond adolescent program ages. The upper age limit of 45 years was chosen based on vaccine licensure as the 9vHPV vaccine is currently authorized for use in females ages 9-45.

Women will not be excluded based on baseline HPV immune status. All women can benefit from vaccination as they are virtually all seronegative for at least one 9vHPV type. Also, HPV seronegativity is not required for vaccination programs, thereby making our findings most relevant to vaccination programs, which would be conducted without a seronegativity requirement. We will assess baseline HPV immune status for use in post hoc outcomes analysis.

2. Randomization

Randomization will be stratified by site using permuted blocks of random size. A CIHR Canadian HIV Trials Network (CTN) statistician will computer-generate random allocations, which will be uploaded to a password-protected webpage. When an eligible consenting participant is identified, the webpage will issue a study identification number and vaccine regimen allocation. An automated audit trail will track date and time of transactions along with study identification number, stratum, and allocation. No placebo will be used as the primary aim of this study is to assess non-inferiority to different 9vHPV vaccine dosing regimens, not to compare outcomes to unvaccinated women.

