6.3.1 Capacity to Consent

The NOVA Study will be enrolling participants between ages 18 and 45. The Capacity to Consent steps below apply to potential participants below the age of majority in their respective province.

After reviewing the consent with the minor, the trial coordinator will assess the minor's understanding of the study by asking them:

1. To explain what they understand about the purpose of the study
2. If they remember approximately how long it will take to complete study visits
3. If they remember what types of samples may be collected at the study visits
4. If they understand one way that their privacy will be protected, (i.e. that unique identifiers will be used on study samples and documents, secure storage etc.)
5. If they understand how much they will be reimbursed for participation in the study
6. If they are aware that they can withdraw from the study at any time
7. If they can point out in the consent form the phone number that could be used to reach the study investigator if they have questions
8. If they understand that the linkage to their provincial cancer registry, and subsequent collection of first name, last name, data of birth, and PHN collected for this purpose is optional.

The trial coordinator will determine that the minor has the capacity to consent if they are able to satisfactorily respond to the above questions and will document whether responses were satisfactory or not. If the minor is not able to respond to the questions in a satisfactory manner, they will be deemed as not having the capacity to consent, the consent process will be halted and the minor will not be offered participation in the study.

4. Source Documentation

A screening log will be kept by each study site, in order to track how many potential participants were approached, how many were not eligible due to having already received an HPV vaccine, and also those who decline participation.

Following collection of informed consent, limited study source documentation should be kept for each participant at the study site. Source data is raw data such as documentation of original observations and activities. Source data is the first time and place an observation is documented, for example the documentation of a urine pregnancy test.

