7.4.1 Study Treatments

Each participant will be followed for a duration of 24 months. Study visits will take place at the site from which each participant is enrolled. Routine clinical exams and blood work will be done as indicated for clinical care with results documented for the study, as appropriate. Participants will be randomly assigned 1:1 to one of two research groups. The Routine Group will have 7 study visits over 2 years at the clinic. The Extended Group will have 6 study visits over 2 years at the clinic.

- **ROUTINE GROUP:** The routine group will receive the HPV vaccine (GARDASIL®9) at the routine vaccine schedule of three doses given at month 0, month 2, and month 6.

- **EXTENDED GROUP:** The extended group will receive the HPV vaccine (GARDASIL®9) at an extended vaccine schedule of three doses given at month 0, month 6, and month 12.

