1. To determine if 2 doses of 9vHPV vaccine are non-inferior to 3 doses in WLWH for the additional 9vHPV types not in the primary outcome, we will evaluate serologic response by comparing peak anti- HPV6/11/31/33/45/52/58 GMTs individually and seroconversion rates with 95% CI at 7 months in both groups using linear and logistic regression, respectively, adjusted for HIV viral load, CD4+ T cell count, and age.
2. As the world is moving towards one-dose HPV vaccine schedules, we will take the opportunity to collect preliminary data on the peak one-dose antibody response at month 1. These data will inform the sample size calculation for a future one-dose trial, as appropriate, and will be reported as anti-HPV16/18 GMTs with 95% CI.
3. To evaluate significant adverse events, the proportion (and 95%CI) of participants who experience significant adverse events will be calculated for the entire study population, and also by group. The types and severities of adverse events will be described.
4. To address vaccine efficacy, we will calculate incidence rates of abnormal cervical cytology and histology (HSIL), and breakthrough persistent HPV infection. HSIL will be described with Kaplan-Meier curves. If sufficient numbers of each are observed, Kaplan-Meier curves will be calculated by age range (21-30, 31-39, 40-55, >55), CD4 count (<200, 200-500, >500), HIV viral load (detectable vs. undetectable), and prior HPV status. Persistent HPV will be described by type of HPV, high vs. low-risk, and vaccine type or not, using Kaplan-Meier curves for HPV acquisition and frequencies and percentage for persistent infections. Given the capability to intervene with early pre-cancerous changes in the cervix, we cannot ethically use cervical cancer as an end point but other efficacy endpoints are critical for an HPV vaccine study as an immune correlate of protection is unknown.
5. To assess the uptake of HPV vaccination of WLWH, a screening log will be kept by each study site to track how many WLWH aged 18-45 were not eligible to participate in the study due to having already received an HPV vaccine. The proportion of women who were previously vaccinated will be calculated for the population of women aged 18-45 at each site and across the country.

6. **Planned Subgroup Analyses**

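### The age bands for the exploratory HSIL curves do not fit the 18-45 eligibility range: ages 18-20 have no band, the >55 band must be empty, and the 40-55 label overstates the ages studied.

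*Protocol*

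**What the plan says.** Protocol 13.5, item 4, covers vaccine efficacy. It plans incidence rates of abnormal cytology and histology and of breakthrough persistent HPV infection, and an overall Kaplan-Meier description of HSIL. It then adds stratified curves under a condition, "If sufficient numbers of each are observed", and gives the age strata: "Kaplan-Meier curves will be calculated by age range (21-30, 31-39, 40-55, >55". CD4 count, HIV viral load and prior HPV status are the other stratifiers. The sentence that follows gives persistent HPV its own breakdown, by HPV type, risk class and whether the type is in the vaccine. Age is not among these.

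Eligibility is fixed elsewhere. The inclusion criterion in 5.0 is "Age 18-45 years", and the Summary gives the same range. Section 5.0 also gives a reason for each limit: "Females aged <18 are excluded because all children, including those with HIV, are vaccinated in adolescent programs in Canada" for the lower one and "The upper age limit of 45 years was chosen based on vaccine licensure" for the upper one. Section 6.3.1 repeats the range: "The NOVA Study will be enrolling participants between ages 18 and 45". On follow-up, 7.4.1 states: "Each participant will be followed for a duration of 24 months".

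**The concern.** A set of age strata should place every eligible participant in exactly one stratum and should describe the people in it. These strata start three years above the lower age limit and run past the upper one. An analyst who follows the text has nowhere to put a woman aged 18-20, must report a stratum that cannot have members, and must label women of 40-45 as 40-55.

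Two things are at stake. The age-banded HSIL curves would omit the ages just beyond the adolescent programmes, although 5.0 says the trial is meant to inform vaccine use beyond those programmes. And a reader of a 40-55 curve could take it as evidence on women up to 55, whom the trial does not enrol. If the bands are left alone, someone will have to re-cut them once data are in hand, which is an avoidable post hoc choice.

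**Working it through.** The protocol states no figure to reproduce here. The check maps each whole year of age to the stated bands.

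**Inputs**
- Bands: 21-30, 31-39, 40-55, >55 (13.5, item 4).
- Eligible age at entry: 18-45 (Summary, 5.0, 6.3.1).
- Follow-up: 24 months (7.4.1).

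**By age at enrolment.** Eligible single years: 45 − 18 + 1 = 28.

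| Band | Years in label | Years that can occur at entry |
|---|---|---|
| none | – | 18, 19, 20 (3) |
| 21-30 | 10 | 21-30 (10) |
| 31-39 | 9 | 31-39 (9) |
| 40-55 | 16 | 40-45 (6) |
| >55 | open-ended | none (0) |

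Years with a band: 10 + 9 + 6 = 25. Years without one: 28 − 25 = 3, so 3/28 = 10.7% of eligible single years. In the 40-55 label, 16 − 6 = 10 years (46-55) cannot occur at entry.

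**By age attained during follow-up.** Item 4 does not say which age is meant, so the other reading was checked too. A woman enrolled at 45 is under 46 at entry and under 48 at month 24, so the oldest attained age is 47 completed years. The 40-55 band then fills at 40-47, which is 8 of its 16 years. The >55 band is still empty, and time spent at ages 18-20 still has no band. A woman enrolled at 18 is under 19 at entry and under 21 at month 24, so she never enters a band. Neither definition of age repairs the bands.

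**The case against.** The best defence is that very little depends on these bands. The stratified curves are exploratory and descriptive, and they are drawn only if numbers suffice. Section 13.3 itself notes that endpoints such as cervical dysplasia take many years to develop, so with 24 months of follow-up the curves may never be produced. An empty stratum changes no estimate, and the 40-55 stratum still contains every woman aged 40-45. All of this stands, and it sets the severity. It does not remove the error: the condition decides whether curves are drawn, not who belongs to which band. Nor is this detail left for a statistical analysis plan, because the protocol prints specific cut points that conflict with its own population.

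It could also be said that 21 is a deliberate floor. No section says so, none excludes ages 18-20 from the efficacy analysis, and a floor would not explain the upper bands.

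Several stronger readings are tempting but not supported:

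- *The youngest women are lost from the efficacy analysis.* They are not. The incidence rates and the overall HSIL curve carry no age restriction.
- *Persistent infection is affected in the same way.* This is ambiguous. The condition could be read to reach both outcomes, but the bands follow directly on the HSIL sentence, and the breakdown given for persistent HPV omits age.
- *About 11% of participants are unclassified.* The 3 of 28 counts years of age, not women. The protocol gives no age distribution.
- *The age subgroups in 13.6 share the fault.* That section names age without bands and contains no error.

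**Conclusion.** The point holds as a minor inconsistency. The stated age bands conflict with the trial's own eligibility range: three eligible years of age have no band, one of the four bands is empty by design, and one label runs ten years past the oldest age at entry. Only the 18-20 gap changes who is analysed, and only in the age-banded HSIL curves; the other two are matters of display and labelling.

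The mapping rests on the enrolment range and the 24-month follow-up as written, and it holds for age at enrolment and for attained age. The number of women aged 18-20 is unknown; that it is probably small is a judgement, not a figure from the protocol. The primary analysis adjusts for age without using these bands, so it is untouched. The statistical analysis plan was not available and may already use other bands; the protocol text would still need to agree with it.

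**What to change.** In 13.5, item 4, replace the age bands with a set that covers 18-45 without gaps, drop >55, and say which age is used. One workable choice is 18-30, 31-39 and 40-45 by age at enrolment. It keeps the existing internal cut points and covers all 28 years (13 + 9 + 6). The documents do not dictate these cut points; any gap-free partition of 18-45 would serve. It would help to make clear in the same sentence whether the strata apply to HSIL alone or also to persistent infection.

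The cost is one line of wording. It changes no data collection, sample size, primary or secondary analysis, and 13.6 can stay as it is. The change should be made before outcome data are examined by age.

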2.0 HYPOTHESIS

We hypothesize that the peak anti-HPV16/18 antibody titer (measured by geometric mean titer; GMT) after 2 doses of 9vHPV vaccine will be non-inferior to peak anti-HPV16/18 antibody titer after 3 doses.

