3.0 OBJECTIVES

The overall goal of the study is to assess whether 2 doses of vaccine are non-inferior to 3 doses. Participants will be randomized 1:1 to receive 3 doses of 9vHPV vaccine at the routine vaccine schedule of 0/2/6 months or at an extended schedule of 0/6/12 months.

1. **Primary Objective**
 - 1) Determine whether peak anti-HPV16/18 geometric mean titers (GMTs) to 2 doses of 9vHPV vaccine are non-inferior to peak anti-HPV16/18 GMTs to 3 doses at month 7.
2. **Secondary Objectives**
 - 2) Compare the antibody persistence at month 24 between the routine and extended vaccine schedule.
 - 3) Elucidate the acceptability of HPV self-sampling among WLWH in Canada.

3. Exploratory Objectives

- 4) Determine whether peak anti-HPV6/11/31/33/45/52/58 GMTs from 2 doses of 9vHPV vaccine are non-inferior to those from 3 doses at month 7.
- 5) Assess peak anti-HPV16/18 GMTs to 1 dose at month 1.
- 6) Describe the incidence, type, and severity of adverse events in WLWH.
- 7) Elucidate the efficacy of 9vHPV vaccination up to month 24 (via persistent HPV infection with 9vHPV types, and cytological and histological HSIL).
- 8) Engage in a BC Cancer Registry linkage to investigate rates of pre-cancer or cancer diagnoses.
- 9) Investigate the role of viral and bacterial co-infection in the development of cervical dysplasia and vaccine breakthrough HPV infection in WLWH
- 10) Assess the uptake of HPV vaccination in WLWH aged 18-45 across Canada prior to study.

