To determine if 2 doses of 9vHPV vaccine are non-inferior to 3 doses in WLWH, we will evaluate serologic response by comparing peak anti-HPV16/18 GMTs individually with 95% CI at 7 months in both groups using linear regression, adjusted for HIV viral load, CD4+ T cell count, and age.⁴⁶ We will similarly compare seroconversion rates in the two groups using logistic regression. Adjusting for age and HIV clinical parameters instead of stratifying by them (they are also unlikely to be importantly imbalanced in a trial this size) can improve sensitivity/power.⁴⁶ Using immunobridging,^{47,48} we will also compare the rate of seroconversion and peak anti-HPV GMTs to previously published two-dose 4vHPV responses in girls and women without HIV²³ and previously published three-dose 9vHPV responses in girls and women without HIV using logistic regression for seroconversion rates and one-sample t-tests for GMT comparisons.^{18,49} Immunobridging is a highly accepted method of evaluating HPV vaccines in different groups when a correlate of protection is unknown and efficacy endpoints such as cervical dysplasia take many years to develop. Level of antibody response after two doses will be described by clinical and demographic variables (age, CD4 count, HIV viral load, HPV DNA or antibody positivity at baseline, and lifetime number of sexual partners) using general linear models.

4. Secondary Analyses

1. To compare differences in antibody persistence, longitudinal GMTs will be compared between the two groups (routine vs. extended dosing interval) to determine if there are differences in the rates of antibody persistence at month 24. We will use mixed-effects linear regression on the log-transformed titers to estimate the rate of decline of antibody titers by time since first vaccine dose. Differences in rates will be compared directly using an interaction term between group and time.

2. To evaluate HPV self-sampling acceptability, quantitative survey results will be summarized as frequencies. Comparisons among subgroups (e.g. by age, region, cultural background, and gender) will be conducted using linear regressions.

5. Exploratory Analyses

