Subgroup analyses by gender (woman, gender-diverse) will be conducted if sample size allows, examining differences in all outcomes by gender. Primary and secondary analyses will be analyzed by clinical and demographic variables including: age, ethnicity, region, CD4+ T cell count, HIV viral load suppression (vs. unsuppressed), and HPV DNA or anti-HPV antibody positivity at baseline.

7. **Sample Size Calculations**

The sample size was calculated based on the primary evaluation of non-inferiority of the immunologic response to 2 vs. 3 doses of 9vHPV vaccine. For ethical reasons, all 2 dose recipients will eventually receive a third dose but we used a dose ranging study design to achieve this end. Using a one-sided alpha = 0.025, a non-inferiority margin of 0.5 based on benchmarks set by Merck for other immunobridging studies leading to licensure,⁴³ a standard deviation of 1.379 calculated from HPV16 GMTs in our prior cohort of WLWH, and 80% power, we would require 205 participants per group (total: 410). Given an anticipated dose completion rate of 90% based on our prior experience, we aim to recruit 225 participants per group to achieve power to detect non-inferiority in peak 2 vs. 3 dose GMT.

At 6 of our 10 sites, there are >900 WLWH who are unvaccinated and eligible for this study, suggesting there are likely ~1800 eligible women at all sites. We therefore anticipate being able to achieve the target sample size of 450 given that 90% of eligible WLWH screened in our precursor study were enrolled.

14.0 **DATA MANAGEMENT**

The data safety and monitoring committee (DSMC) will be coordinated through established processes by the CTN and will function at pre-specified intervals to monitor the conduct and progress of the trial, evaluate the accumulating study data including all serious adverse events, recommend protocol changes, alert trial leaders to emerging procedural or ethical issues, and monitor enrolment to ensure timely conduct of the trial. All up to date adverse events will be reported to the DSMC at each meeting to ensure participant safety. All other data including immunogenicity, efficacy, and self-sampling acceptability will be reported to the DSMC as it becomes available throughout the study for assessment of study conduct and progress. Reports from the data management process will be provided to the DSMC to ensure data quality.

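### The 80% power in section 13.7 is for one test on HPV16 and is not the power of the primary claim, which covers HPV16 and HPV18

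*Protocol*

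**What the plan says.** Section 2.0 puts forward one hypothesis for both types: the peak anti-HPV16/18 titre after two doses "will be non-inferior to peak anti-HPV16/18 antibody titer after 3 doses". The primary objective in section 3.0 has the same scope. Section 13.3 makes the primary analysis a matter of "comparing peak anti-HPV16/18 GMTs individually with 95% CI at 7 months", so there are two comparisons, one per type.

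Section 13.7 says the sample size was calculated for the primary evaluation of non-inferiority. Its inputs and result are:

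- Significance level: 0.025, one-sided.
- Margin: "a non-inferiority margin of 0.5 based on benchmarks set by Merck".
- Variability and power: "a standard deviation of 1.379 calculated from HPV16 GMTs in our prior cohort of WLWH, and 80% power".
- Result: 205 in each group, 410 in all.

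Recruitment is then set at 225 per group on an expected 90% completion rate. The section gives no SD for HPV18, no correlation between the two titres, no log base for the margin or the SD, and no assumed true difference. Neither 13.3 nor 13.7 says in so many words that both types must meet the margin.

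**The concern.** A power figure belongs to a decision rule. The hypothesis, as worded, is met only if HPV16 and HPV18 are both non-inferior, and the chance of passing two tests is lower than the chance of passing one unless the two estimates are perfectly correlated. Section 13.7 gives the chance of passing the HPV16 test and presents it as the power of the primary evaluation.

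Two things are at stake. Readers and funders take 80% as the chance that the trial supports a two-dose schedule if that schedule is truly non-inferior, and the calculation does not show this. Also, if HPV16 clears the margin and HPV18 does not, the protocol does not say outright how the primary result is to be read. Section 1.0 treats this peak-titre endpoint as sufficient for regulators to change how the vaccine is recommended, so that reading should be settled before the data are seen.

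**Working it through.** **Inputs from section 13.7:** one-sided alpha 0.025 (z = 1.960), power 80% (z = 0.842), margin 0.5, SD 1.379 (HPV16), 205 per group. Allocation is 1:1 (section 3.0).

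**Assumptions, not in the protocol:** HPV18 SD equal to the HPV16 SD, true difference zero unless stated, and between-type correlation ρ from 0 to 0.9. The normal approximation is used throughout.

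**Step 1. Reproduce 205.** n per group = 2 × SD² × (1.960 + 0.842)² / margin². The numerator is 2 × 1.379² × 2.802² = 29.85.

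| Reading of the margin | Margin | n per group |
|---|---|---|
| Difference of 0.5 in log titre | 0.500 | 29.85 / 0.2500 → 120 |
| Ratio of 0.5, natural log | ln 2 = 0.693 | 29.85 / 0.4805 → 63 |
| Ratio of 0.5, log10 | log10 2 = 0.301 | 29.85 / 0.0906 → 330 |

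None gives 205. With SD 1.379, 80% power at 205 corresponds to an effective margin of 2.802 × 1.379 × √(2/205) = 0.382. An unstated true difference of 0.500 − 0.382 = 0.118 would produce that on the first reading. On the second, a true two-dose to three-dose ratio of about 0.73 would do so: exp(−(0.693 − 0.382)) = 0.73.

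**Step 2. Joint power if 205 gives 80% per type, as stated.** Each test statistic is normal with mean 1.960 + 0.842 and unit variance. Joint power is P(Z₁ < 0.842 and Z₂ < 0.842) for a bivariate normal with correlation ρ.

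| ρ | 0 | 0.5 | 0.7 | 0.9 |
|---|---|---|---|---|
| Joint power | 64.0% | 68.7% | 71.3% | 75.0% |

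At ρ = 0 this is 0.80 × 0.80. It reaches 80% only at ρ = 1.

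**Step 3. Joint power at 205 from the printed inputs.** The standard error of the difference is 1.379 × √(2/205) = 0.1362. Power per type is Φ(margin / 0.1362 − 1.960).

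| Reading | Per type | ρ = 0 | ρ = 0.5 | ρ = 0.7 | ρ = 0.9 |
|---|---|---|---|---|---|
| Difference of 0.5 | Φ(1.71) = 95.6% | 91.5% | 92.3% | 92.9% | 94.0% |
| ln 2 | Φ(3.13) = 99.9% | 99.8% | 99.8% | 99.8% | 99.9% |
| log10 2 | Φ(0.25) = 59.9% | 35.8% | 43.8% | 47.6% | 52.9% |

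**Step 4. Sensitivity to the unstated inputs.** On the first reading with independent types, an HPV18 SD of up to 1.72 (about 25% above 1.379) keeps joint power at 80%. If that margin is in natural-log units and the true ratio is 0.9 rather than 1, power per type is Φ((0.500 − 0.105) / 0.1362 − 1.960) = 83%. Joint power is then 68% at ρ = 0 and 78% at ρ = 0.9.

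**The case against.** The best defence is that the trial may have power to spare. On two of the three readings of the margin, the printed inputs need only 120 or 63 per group, and at 205 both types pass with probability above 90%. That arithmetic stands. It rules out reporting 64–75% as this trial's established power. It does not rescue the stated 80%, because the reserve depends on a true ratio of exactly 1, an HPV18 SD no worse than modestly larger, and a scale the protocol does not give. On log10, HPV16 alone falls short.

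A second defence is that rules for combining two antigens are often left to a statistical analysis plan, which is not at hand. That is fair for the detail of a multiplicity method, and its absence is not the point here. The point is a numerical power statement, printed in the protocol, whose scope does not match the printed primary hypothesis.

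A reader might infer more: that an alpha of 0.025 and a power of 80% are incompatible for this pair of tests, or that the false-positive rate is inflated. The documents support neither. On two readings both error rates are met together. Inflation would need a rule under which passing on either type suffices, and the protocol adopts no such rule. The wording of the hypothesis points to both types being required, and then each test at one-sided 0.025 needs no adjustment.

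**Conclusion.** The point stands as a mismatch between the stated power and the primary claim. The 80% in section 13.7 belongs to a single HPV16 comparison, while the claim concerns HPV16 and HPV18. If the protocol's own 80% is accepted for each type, the power for the claim is 64–75% for correlations from 0 to 0.9. Those correlations are assumptions, as is equal power for HPV18.

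The actual joint power cannot be determined from the protocol, because 205 is not reproduced by the printed inputs. Step 3 spans about 36% to above 99%, depending on the scale alone. A shortfall is therefore possible but not demonstrated. The HPV18 SD could move the figure either way, since it may be smaller or larger than 1.379.

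**What to change.** In section 13.3, state that the primary claim requires both HPV16 and HPV18 to clear the margin, each tested at one-sided 0.025 with no alpha adjustment.

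In section 13.7:

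- state the scale of the margin and of the SD, including the log base, and the assumed true two-dose to three-dose ratio;
- give the HPV18 SD from the same prior cohort as the HPV16 value;
- replace the 80% figure with the joint power for both types at the planned size, with the correlation assumed or a range of correlations.

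This costs a sentence and a recalculation. It requires no extra participants and no change to procedures. The downside is that the restated power may be less favourable than 80%.
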